**Table 2. Definition of RIFLE Criteria**

Term	Definition
Risk (R)	Increased creatinine level 1.5× or GFR decrease >25%
Injury (I)	Increased creatinine level 2× or GFR decrease >50%
Failure (F)	Increased creatinine level 3×, GFR decrease >75%, or creatinine level ≥4 mg/dL
Loss (L)	Persistent acute renal failure or complete loss of function for >4 weeks
ESKD (E)	ESKD for >3 months

ESKD = end-stage kidney disease; GFR = glomerular filtration rate; RIFLE = Risk–Injury–Failure–Loss–End-stage renal disease.

The number and percentage of patients reporting adverse events of special interest will be summarized by each category and treatment group in Part A in the Safety and CE Populations. In addition, proportion of patients with nephrotoxicity will be compared between the investigational and control groups using Chi-square test. The Chronic hemodialysis patients will not be included in the nephrotoxicity analysis.

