**Table 1. Study Drug Dose Adjustments by Renal Function**

Estimated Creatinine Clearance, mL/min (Cockcroft-Gault)	ETX2514SUL Dosage Regimen	Colistin Dosage Regimen	Imipenem/Cilastatin Dosage Regimen [1]
130-200 (augmented renal clearance)	1.5/1.5 g q6h	2.5 mg/kg q12h	1.0/1.0 g q6h
90-129 (normal)	1.0/1.0 g q6h	2.5 mg/kg q12h	1.0/1.0 g q6h
60-89 (mild renal impairment)	1.0/1.0 g q6h	1.25 to 1.9 mg/kg q12h	0.75/0.75 g q8h
30-59 (moderate renal impairment)	1.0/1.0 g q6h	1.25 mg/kg q12h or 2.5 mg/kg once daily	0.5/0.5 g q6h
15-29 (severe renal impairment)	1.0/1.0 g q8h	1.5 mg/kg q36h	0.5/0.5 g q12h
0-14 (severe renal impairment) [2]	1.0/1.0 g q12h	1.5 mg/kg q36h	0.5/0.5 g q12h
Intermittent hemodialysis	1.0/1.0 g q12h [4]	Non-dialysis day: CBA dose of 65 mg q12h. Dialysis day supplement: add 40 mg (for 3-hour IHD session) or 50 mg (for 4-hour IHD session) post-dialysis [3]	0.5/0.5 g q12h [4]
Continuous renal replacement therapy	1.5/1.5 g q6h	220 mg q12h	1.0/1.0 g q8h to q12h, depending on ultrafiltration rate

 
Administer doses ≤0.5 g by IV infusion over 20 to 30 minutes. Administer doses >0.5 g by IV infusion over 40 to 60 minutes. In patients who develop nausea during the infusion, the rate of infusion may be slowed.
 
Patients with creatinine clearance <15 mL/min should not receive imipenem/cilastatin unless renal replacement therapy of acute hemodialysis is instituted within 48 hours of dosing.
 
The dialysis session should occur toward the end of a colistimethate dosing interval, and the supplement to the baseline (non-dialysis) daily dose should be administered with the next regular dose, after the dialysis session has ended.
 
The dialysis session should occur toward the end of a dosing interval, and the daily dose should be administered after the dialysis session has ended.
 
 
CBA = colistin base activity; ETX2514SUL = sulbactam-ETX2514; IHD = intermittent hemodialysis; IV = intravenous; q6h = every 6 hours; q8h = every 8 hours; q12h = every 12 hours; q36h = every 36 hours.
			

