#### 9.2.4 Analysis of Safety

All patients who receive any amount of study drug (MITT Population) will be included in the safety analyses. Patients who received the wrong study drug for their entire course of treatment will be analyzed in the group based on the drug received.

A primary analysis of safety will be performed for Part A to assess the proportion of patients with nephrotoxicity, as measured by the RIFLE criteria based on the Safety and CE Populations.

Overall safety will be assessed for Part A and Part B in the Safety Population. The number and percentage of patients in each treatment group reporting at least 1 occurrence of a TEAE for each unique system organ class and preferred term will be tabulated. A TEAE is defined as an adverse event occurring on or after the administration of the first dose of study drug. Treatment-emergent adverse events will also be tabulated by treatment group, severity, and the relationship to study drug as assessed by the Investigator. The number and percentage of patients in each treatment group reporting at least 1 occurrence of a treatment-emergent SAE will be tabulated. The number and percentage of patients (in each treatment group) prematurely discontinuing study drug treatment due to a TEAE will be tabulated by system organ class and preferred term. Adverse events of special interest in Part A will be summarized for all patients by treatment.

Safety laboratory data will be presented by descriptive statistics of the post-baseline value and the change from baseline, as well as the number and percentage of patients with potentially clinically significant laboratory values. Descriptive statistics of vital signs and ECG parameters and the change from baseline will also be presented. An outlier analysis of the ECG parameters will be conducted.

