### 2.1. Primary Objectives

The primary objectives of this study are the following:

- To compare the efficacy of Sulbactam-ETX2514 (ETX2514SUL) plus imipenem/cilastatin to colistin plus imipenem/cilastatin in patients with carbapenem-resistant *Acinetobacter baumannii-calcoaceticus* complex (CRABC) infections in Part A; and
- To compare the incidence of nephrotoxicity, as measured by the Risk-Injury-Failure-Loss-End-stage renal disease (RIFLE) criteria, of ETX2514SUL to colistin in patients with ABC infections in Part A.

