#### Adverse Events of Special Interest

Adverse events of special interest and their definitions include the following:

- Allergic and hypersensitivity reactions: Severe and serious adverse drug reactions from the Medical Dictionary for Regulatory Activities (MedDRA) Standardized MedDRA Queries of allergy and hypersensitivity,
- Nephrotoxicity: Using the RIFLE criteria for the duration of the study (see Table 2)1, and

- Emergent infections and superinfections: All serious and severe events in the MedDRA system organ class of infections and infestations other than the indication infection (ie, ABC).
- Clostridioides difficile infection

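### The RIFLE Failure limb at creatinine ≥4 mg/dL needs no rise from baseline, so a stable Part A patient who enters at that level counts as nephrotoxicity

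*SAP*

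**What the plan says.** One of the two primary objectives (SAP Section 2.1) is "To compare the incidence of nephrotoxicity, as measured by the Risk-Injury-Failure-Loss-End-stage renal disease (RIFLE) criteria, of ETX2514SUL to colistin" in Part A. Protocol Section 9.2.4 adds: "A primary analysis of safety will be performed for Part A to assess the proportion of patients with nephrotoxicity". The analysis uses the Safety and CE Populations. Below SAP Table 2, the test is given as "proportion of patients with nephrotoxicity will be compared between the investigational and control groups using Chi-square test".

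SAP Table 2 and Protocol Table 6 define Failure in the same words: "Increased creatinine level 3×, GFR decrease >75%, or creatinine level ≥4 mg/dL". The first two limbs are changes. The third, "or creatinine level ≥4 mg/dL", is an absolute level with no reference to baseline. The time window is set by "Nephrotoxicity: Using the RIFLE criteria for the duration of the study", without an express limit to values after the first dose. SAP Section 9.1.3 defines baseline as the last value before the first dose, but nothing ties the 4 mg/dL limb to it.

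The one exclusion from the analysis is "The Chronic hemodialysis patients will not be included in the nephrotoxicity analysis".

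The exclusion criteria in Protocol Section 4.2 set no upper limit on creatinine and no lower limit on creatinine clearance. SAP Section 9.2.3 plans baseline clearance categories below 15 and from 15 to below 30 mL/min. SAP Section 9.3.4 plans a subgroup below 30 mL/min for the primary efficacy endpoint, which exists only in Part A.

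**The concern.** The comparison is meant to measure kidney injury that arises on treatment. For a patient already at 4 mg/dL, the absolute limb measures the state at entry. A patient who starts at 4.2 mg/dL and remains there meets Failure, the most severe of the creatinine-based classes, at 1.00 times baseline. The SAP accepts the principle by removing chronic hemodialysis patients, but it leaves in the non-dialysed patients to whom the same reasoning applies.

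The stake is the readability of a primary-objective result. Events that neither regimen caused raise the reported incidence in both arms and blur the contrast between them.

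**Working it through.** **Analysis size.** The plan states no event rate or power for nephrotoxicity. Its only powered figure is 120 CRABC m-MITT patients for mortality. At 60 per arm with 36% vs 41% and a 20-point margin, SE = √[(0.41×0.59 + 0.36×0.64)/60] = 0.0887, and power = Φ(0.25/0.0887 − 1.96) = 80.5%, which matches the stated 80%. Enrolment is 120/0.60 = 200, or about 100 per arm. I use 100 per arm below as an approximation to the Safety Population. Nothing else here depends on the mortality calculation.

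**What the limb does, by baseline creatinine (mg/dL).**

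| Baseline | Level needed for 1.5× / 2× / 3× | Ratio to baseline at 4.0 |
|---|---|---|
| 2.0 | 3.0 / 4.0 / 6.0 | 2.00 |
| 3.0 | 4.5 / 6.0 / 9.0 | 1.33 |
| 3.5 | 5.25 / 7.0 / 10.5 | 1.14 |
| 4.0 | 6.0 / 8.0 / 12.0 | 1.00 |

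- Failure with no rise at all requires a baseline of 4 mg/dL or more.
- Failure without a 1.5-fold rise requires a baseline above 4/1.5 = 2.67 mg/dL.
- If GFR moves inversely with creatinine, the GFR fall on reaching 4 is 1 − baseline/4. This exceeds 25% only for a baseline below 3.0. Between 2.67 and 3.0 the GFR limb would therefore already give Risk, and the absolute limb only raises the grade.

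**Who has a creatinine of 4 mg/dL.** Cockcroft-Gault: (140 − age) × weight / (72 × 4), times 0.85 for women. At age 60 and 70 kg this is 80×70/288 = 19.4 mL/min for men and 16.5 for women. Over ages 40 to 80 and 50 to 90 kg the range is 8.9 to 31.2, essentially the severe-impairment rows of Protocol Table 1.

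**Dilution.** Let b be the share of analysed patients who enter at ≥4 mg/dL and are counted for that reason, and p the true rate in the others. The observed rate is b + (1−b)p, so the difference is (1−b) times the true one. The documents give neither b nor p, so all values here are assumptions. With 20% vs 40%:
- b = 2%: 21.6% vs 41.2%, difference 19.6 points.
- b = 5%: 24.0% vs 43.0%, difference 19.0 points.

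**Power.** With n = 100 per arm, difference d and mean rate m, power = Φ{[d − 1.96√(2m(1−m)/n)] / √([p₁(1−p₁)+p₂(1−p₂)]/n)}. For 20% vs 40%:
- b = 0: (0.200 − 0.1270)/0.0632 = 1.154, power 87.6%.
- b = 2%: (0.196 − 0.1286)/0.0642 = 1.050, power 85.3%.
- b = 5%: (0.190 − 0.1308)/0.0654 = 0.905, power 81.7%.

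Range over other assumed rates (difference in points, power):

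| True rates | b = 0 | b = 2% | b = 5% |
|---|---|---|---|
| 25% vs 50% | 25.0, 96.0% | 24.5, 95.0% | 23.75, 93.4% |
| 20% vs 40% | 20.0, 87.6% | 19.6, 85.3% | 19.0, 81.7% |
| 15% vs 30% | 15.0, 72.2% | 14.7, 68.4% | 14.25, 63.0% |

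For comparison, leaving these patients out altogether (20% vs 40%) keeps the 20-point difference and gives power of 86.9% at b = 2% and 85.9% at b = 5%.

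**Chance imbalance.** The between-arm difference in the share entering at ≥4 mg/dL has SD √(2b(1−b)/100), which is 2.0 points at b = 2% and 3.1 points at b = 5%.

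**The case against.** The strongest reply is that the documents already contain a new-or-worsened principle. Nephrotoxicity is listed as an adverse event of special interest, treatment-emergent events start at the first dose (SAP Section 9.4.1), and Protocol Section 8.1 says that conditions present at Screening are not reported as adverse events unless they change. But that text governs what investigators report. Table 2 is a laboratory rule, and nothing in it or around it makes the 4 mg/dL limb subject to that principle. How it will be programmed is unknown, but the rule as written gives the wrong class.

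A second reply is that few patients are involved and that randomization balances them in expectation. Both parts are fair. Neither arm is favoured systematically, and the numerical effect is modest.

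A third is that Protocol Table 1 is a daily dose-adjustment table, so its low-clearance rows do not prove entry at those levels. That is also fair. Entry rests on the absence of any renal limit for Part A and on the baseline categories and subgroup planned in the SAP.

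Three stronger inferences are tempting, and the documents do not support them:
- **Renally impaired patients in general are miscounted.** A stable patient is caught only at a baseline of 4 mg/dL or more. Mild and moderate impairment are essentially unaffected.
- **Such patients become events on Day 1.** The scheduled Day 1 creatinine is pre-dose (Protocol Section 6.3.1) and can itself be the baseline. The first scheduled post-dose value is Day 2. The open-ended time window allows a Day 1 reading but does not establish it.
- **Patients on acute renal replacement therapy are expected in the comparison.** Protocol Section 4.1.3 directs patients with acute kidney injury on such therapy to Part B, and Section 4.2 excludes peritoneal dialysis from the study. What remains is a gap: no Part A exclusion names renal replacement therapy.

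**Conclusion.** The point holds for a defined group. A non-dialysed Part A patient who enters at ≥4 mg/dL and does not worsen is a nephrotoxicity Failure under the stated rule, and patients entering above 2.67 mg/dL can be graded Failure without a 1.5-fold rise. The result is inflated incidence in both arms and a risk difference reduced by (1−b).

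If b is 2% to 5% and the true rates are 20% vs 40%, the loss is 0.4 to 1.0 point of a 20-point difference and 2.3 to 5.9 points of power. These sizes rest on assumed b and rates, on about 100 patients per arm, and on any RIFLE class counting as nephrotoxicity in the Chi-square test. The defect does not threaten the comparison. It is still a wrong classification in a primary-objective analysis, and it is cheap to correct before unblinding.

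**What to change.** Add the following under SAP Table 2 and align Protocol Table 6:
- Apply RIFLE to creatinine values after the first dose only.
- Count the ≥4 mg/dL limb only when baseline is below 4 mg/dL and creatinine has risen from the SAP baseline by a pre-set minimum. Judge patients with a baseline of 4 mg/dL or more on the relative limbs alone.
- Extend the chronic hemodialysis exclusion to any Part A patient on renal replacement therapy at baseline, since dialysis then drives the creatinine.

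A sensitivity analysis leaving out patients with a baseline of 4 mg/dL or more would show how much the rule matters.

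The cost is a few sentences in two documents and no new data. A few patients may leave the denominator, and the Failure count may be slightly lower.

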### 5.2 Rationale for Dosing

The doses of ETX2514 and sulbactam to be evaluated in this study have been selected based on Phase 1 and Phase 2 PK, safety, and efficacy data and extensive PK/PD modeling and probability of target attainment against CRABC in the lung. Data from these studies and details of the PK/PD modeling are provided in more detail in the Investigator's Brochure.

ETX2514 1.0 g was generally well tolerated in all of the clinical studies to date. Sulbactam 1.0 g was generally well tolerated in the Phase 2 study. The total daily dose of sulbactam being used in the current study is consistent with the US Product Circular for Unasyn, in which the maximum approved daily dose in patients with normal renal clearance for sulbactam is 4 g, which is equivalent to 1.0 g sulbactam q6h.

The ETX2514SUL regimen of 1.0 g ETX2514/1.0 g sulbactam should be infused over 3 hours q6h given for 7 days to 14 days (28 doses to 56 doses), depending on the clinical response.

Imipenem/cilastatin will be administered as a 1.0 g/1.0 g dose infused over 1 hour q6h given for the same duration as ETX2514SUL or colistin.

Colistin will be administered at a daily dose of 5 mg/kg of colistin base activity (CBA) divided into 2 doses 12 hours apart. Doses will be adjusted to ideal body weight in obese patients. Patients who weigh <60 kg with normal renal function will receive a flat dose of 300 mg CBA or 9 million international unit (MIU)/day. A single loading dose of 2.5 to 5 mg/kg (total dose not exceeding 300 mg CBA or 9 MIU and following local standard of care) given IV over 3 to 6 minutes (or according to standard of care) will be administered on Day 1. Colistin infusions beyond the loading dose on Day 1 will begin 12 hours after the initial loading dose and will be infused over 30 minutes. Details on dosing for those patients who are on colistin prior to randomization into the study can be found in the Pharmacy Manual.

Details of study drug preparation and administration can also be found in the Pharmacy Manual.

No dosing regimen changes, other than those specified in the protocol for renal insufficiency (see [Section 5.3](#)) or for patients on imipenem who develop a seizure that is thought to be directly related to imipenem, can occur without discussion with the Medical Monitor.

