### **3.3. Randomization and Blinding**

Qualifying patients enrolling in Part A will be randomized in a 1:1 ratio to receive 1.0 g ETX2514/1.0 g sulbactam q6h plus 1.0 g imipenem/1.0 g cilastatin q6h or 2.5 mg/kg colistin q12h plus 1.0 g imipenem/1.0 g cilastatin q6h via the Interactive Response Technology (IRT) system. Patients enrolled in the study based on the positive BPP rapid test results but are found to not grow ABC in respiratory specimen cultures by the local microbiology laboratory will be withdrawn from the study drug treatment as detailed in Protocol Section 4.3.

Randomization in Part A will be stratified by indication (HABP/VABP/VP versus bacteremia), severity of illness (based on APACHE II [10 to 19 versus 20 to 30], SOFA [7 to 9 versus  $\geq 10$ ], or qSOFA [2 versus 3] score at Screening), and geography (China Mainland versus Rest of World). In the situation where a patient has more than one score reported, the scores will be used in the following order: APACHE, SOFA, and qSOFA. A quick reference guide will be provided that describes the IRT system and includes user instructions.

The study data will be collected and handled as if it were a blinded study. The blinded assessor (see Section 3.3.2), the Sponsor, and the Sponsor's designees involved in medical and safety monitoring, data management, and other aspects of the study (eg, interpretation of the results) will be blinded to treatment assignment. Given the complexity of the regimens, the Principal Investigator, other care givers, the clinical research associate (CRA), and other site personnel (eg, study coordinators and pharmacy staff) will be unblinded (see Section 3.3.1). Patients will not be informed of their treatment assignment, and efforts will be made to keep patients naïve to their treatment throughout the course of the study.

Part B is open-label and not randomized; all patients enrolling in Part B will receive 1.0 g ETX2514/1.0 g sulbactam q6h plus 1.0 g imipenem/1.0 g cilastatin q6h.

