### 9.2.3. Demographic and Baseline Characteristics

Demographics and baseline characteristics including age (as a continuous variable and categorized as <65, 65-75 and >75 years), sex, race, ethnicity, weight, body mass index (BMI) (as a continuous variable and categorized as <25, 25-<30, 30-<35 and  $\geq$ 35), creatinine clearance (as a continuous variable and categorized as <15 mL/min, 15-<30 mL/min, 30-<60 mL/min, 60-<90 mL/min and  $\geq$ 90 mL/min), Charlson Comorbidity Index <3 or  $\geq$ 3, septic shock status at baseline, mechanical ventilation status at baseline, infection type (bacteremia, HABP, VABP, VP, cUTI, AP, surgical wound infection, and post-traumatic wound infection), APACHE II score [<10, 10 to 19, 20 to 30 and >30], SOFA score [<7, 7 to 9 and  $\geq$ 10], qSOFA score [<2, 2, 3 and >3], severity of illness (APACHE II [10-19]/SOFA [7-9]/qSOFA [2] and APACHE II [20-30]/SOFA [ $\geq$ 10]/qSOFA [3]) will be summarized by treatment group and baseline infection type (Overall, Bacteremia, HABP, VABP, VP, cUTI, AP, Surgical Wound Infection, and Post-traumatic Wound Infection) in the ITT, m-MITT, and CRABC m-MITT Populations. The demographics and baseline characteristics will be summarized for all regions and repeated for Mainland Chinese patients.

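### The nephrotoxicity primary objective rests on an unadjusted chi-square test alone: valid, but with no risk difference or confidence interval and no pre-specified use of baseline creatinine clearance

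*SAP*

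**What the plan says.** SAP 2.1 lists two primary objectives for Part A. The second begins "To compare the incidence of nephrotoxicity, as measured by the" RIFLE criteria. Protocol 9.2.4 gives it matching status: "A primary analysis of safety will be performed for Part A to assess the proportion of patients with nephrotoxicity", in the Safety and CE Populations.

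SAP 9.4.1 (Adverse Events of Special Interest, below Table 2) summarizes counts and percentages in those two populations. It then states that the "proportion of patients with nephrotoxicity will be compared between the investigational and control groups using Chi-square test". Chronic hemodialysis patients are left out. No effect estimate, interval, covariate, stratum or sensitivity analysis is named.

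The RIFLE tiers in SAP Table 2 are mostly relative changes. The lowest reads "Increased creatinine level 1.5× or GFR decrease >25" percent. One limb of the Failure tier is an absolute level: "creatinine level ≥4 mg/dL".

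On allocation, SAP 3.3 says: "Randomization in Part A will be stratified by indication (HABP/VABP/VP versus bacteremia), severity of illness", plus geography. Renal function and prior colistin are not factors.

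Baseline renal function appears in two other places. SAP 9.2.3 tabulates "creatinine clearance (as a continuous variable and categorized as <15 mL/min" and upward, by arm, in the ITT, m-MITT and CRABC m-MITT Populations. SAP 9.3.4 uses CrCl groups as a subgroup factor, for the mortality endpoint only.

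Protocol 5.2 foresees some exposure to colistin before the study: "Details on dosing for those patients who are on colistin prior to randomization into the study can be found in the Pharmacy Manual".

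**The concern.** The SAP treats its other comparisons more fully. The primary mortality endpoint has a difference with a two-sided 95% CI (9.3.1), a list of sensitivity analyses and a set of subgroups. Every secondary rate comparison has a 95% CI for the difference (9.3.2). Nephrotoxicity, also a primary objective, gets a p-value.

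Baseline renal function is a natural covariate for a kidney endpoint. It sets the dose of study drugs (Protocol Table 1), and a patient who starts with a high creatinine reaches the absolute 4 mg/dL limb after a smaller relative rise. If the arms differ by chance in baseline CrCl, readers will ask what the comparison looks like within CrCl groups. As written, any answer would be chosen after seeing the data, on a primary objective. A p-value alone also does not tell the reader how large the difference is or how well it is estimated.

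**Working it through.** **1. The plan's own figure.** The only sizing in the documents is for mortality (SAP 4): 41% versus 36%, margin 20 points, 80% power, two-sided 95% CI. With unpooled variance:

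n per arm = (1.960 + 0.842)² × (0.41×0.59 + 0.36×0.64) / (0.20 + 0.05)² = 7.849 × 0.4723 / 0.0625 = 59.3, so 60 per arm and 120 in total (power 80.5%). Then 120 / 0.60 = 200 enrolled.

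This reproduces. It says nothing about nephrotoxicity power, but 1:1 allocation of about 200 patients gives roughly 100 per arm for the safety comparison. The documents give no nephrotoxicity rate, no gradient by CrCl and no share of patients with low CrCl, so every risk below is an assumption.

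**2. How far can a chance imbalance move the estimate?** Assume 40% of patients have CrCl below 60 mL/min.

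- SD of the between-arm difference in that share: √(2 × 0.4 × 0.6 / 100) = 0.069, or 6.9 points.
- 95% range: ±1.96 × 6.93 = ±13.6 points.
- Shift in the crude risk difference at that limit = 13.6 × risk gap between renal strata. This gives 1.4, 2.7 and 4.1 points for gaps of 10, 20 and 30 points.

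With risks of 20% and 40% in the two renal strata, the overall risk is 28%. The standard error of the risk difference is then √(2 × 0.28 × 0.72 / 100) = 6.3 points. Imbalance accounts for (6.93 × 0.20)² / 6.35² ≈ 4.8% of its variance. Letting the impaired share run from 20% to 50% and the gap from 10 to 40 points, this fraction is 1% to 17%, and at most 7% unless the gap is 40 points. The chi-square's standard error already contains it.

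**3. Type I error.** Simulation: 200,000 trials, 100 per arm, two renal strata, two-sided 5%. Across impaired shares of 20%, 40% and 50% and gaps of 10 to 40 points, type I error was 4.9–5.2% for the chi-square and 4.9–5.1% for the Cochran-Mantel-Haenszel (CMH) test. Both are valid. The difference is conditional. In the roughly 4–6% of trials with an imbalance of at least 1.96 SD, the chi-square's error was 5–9% for gaps of 10 to 25 points and 12–14% for a 40-point gap. The stratified test stayed near 5%.

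**4. Power.** 100 per arm, 40% with low CrCl. Risks are shown as (higher CrCl, low CrCl):

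| Gap in colistin arm | Colistin risks | ETX2514SUL risks | Chi-square | CMH |
|---|---|---|---|---|
| 10 points | 30%, 40% | 15%, 25% | 68% | 68% |
| 20 points | 25%, 45% | 12%, 28% | 66% | 68% |
| 30 points | 20%, 50% | 10%, 30% | 63% | 67% |
| 50 points | 15%, 65% | 5%, 45% | 60% | 72% |

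A second set with a common odds ratio of 0.4 and impaired shares of 20% to 50% gave a change of −0.4 to +2.3 points for gaps of 10 to 25 points, and +4.5 to +6.3 points for a 40-point gap.

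These runs used two renal strata. The three strata proposed under the fix were not simulated.

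**The case against.** The strongest reply is that the planned test is sound and the rest is preference. Allocation is randomized, so CrCl is balanced in expectation even though it is not a stratification factor, and type I error holds. The mortality analysis is unadjusted too. RIFLE is scored mainly against each patient's own pre-dose value, so baseline is not ignored. Chronic hemodialysis patients are removed, and patients with acute kidney injury on renal replacement at entry are a Part B group. CrCl by arm is tabulated in ITT, which differs from the Safety Population only by untreated patients, so a marked imbalance would probably be seen.

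All of this stands, and it rules out calling the comparison biased. It does not answer the missing estimate and interval, which the SAP supplies for mortality and the secondary rates. Nor does it supply an adjusted analysis fixed in advance. The reply is also weaker for the CE summary: CE selects on doses received and on response after randomization (SAP 8.5), and CrCl is not tabulated there.

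A reader might also infer that pre-study colistin tilts the result against ETX2514SUL, because late kidney injury from it would be counted against the assigned arm. The documents do not support a between-arm bias. That exposure precedes randomization, potentially effective prior therapy is capped at 48 hours unless the patient is failing it (Protocol 4.1.1), and patients failing colistin or polymyxin B cannot enter Part A (Protocol 3.1). The documents do not say how common the remaining exposure is. Stratifying by it would not stop late injury being counted in the assigned arm.

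**Conclusion.** The point holds as one of precision and pre-specification. A primary objective is analysed with a valid test that yields no effect estimate or interval and makes no use of a relevant covariate already collected. The gain from stratifying is modest: about 0 to 4 power points for assumed renal risk gaps of 10 to 30 points at 100 per arm. It is tempting to quote the 12-point gain in the last row of the table, but that needs an assumed 50-point gap between renal strata, and nothing in the documents indicates a gradient of that size. The firmer reasons to act are the missing interval and the lack of an adjusted analysis chosen before the data are seen. The omissions can be read directly in the SAP. The magnitudes rest wholly on assumed rates.

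**What to change.** In SAP 9.4.1:

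- Report the nephrotoxicity risk difference (ETX2514SUL minus colistin) with a 95% CI.
- Alongside the chi-square, pre-specify a CMH test with a Mantel-Haenszel risk difference and 95% CI, stratified by baseline CrCl (<60, 60–<90, ≥90 mL/min). These groups are formed by collapsing the SAP 9.2.3 categories.
- State in advance which of the two is the main analysis. Keeping the chi-square in that role is acceptable.

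In SAP 9.2.3 and 9.2.6, tabulate baseline CrCl and prior polymyxin use by arm in the Safety and CE Populations. An analysis stratified by prior polymyxin use is optional and supportive only. The start and stop times of antibiotics in the 14 days before first dose are already recorded (Protocol 5.6.4).

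The cost is SAP wording and a few lines of code. No new data are needed.
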